2.5. Subject Selection and Enrollment

2.5.1. Study Population and Eligibility

Subjects will undergo baseline evaluation to determine eligibility for the study.

After being informed of the nature of the study, the subject will sign a written informed consent form (ICF) that has been approved by the IRB/EC of the clinical site and by the Sponsor. Subjects will be considered for the study if they meet the specific inclusion/exclusion criteria. The criteria for enrollment must be followed explicitly.

2.5.2. Inclusion Criteria

1. Subject must be aged >18 years.
2. Subject must have signed a written Informed Consent form to participate in the study, prior to any study related procedures.
3. Subject must be willing to comply with the protocol requirements.
4. Subject receives a de novo ablation procedure for treatment of atrial fibrillation.

2.5.3. Exclusion Criteria

1. Pregnant women.

2.5.4. Withdrawal

Every effort should be made to retain subject enrolment for the duration of the study. During the informed consent process subjects should be fully informed of the data collection requirements and duration and should only be enrolled if willing to fully participate in it. All subjects enrolled in the clinical study must be accounted for and documented. Reasons for withdrawal may include;

- Physician discretion
- Subject choice to retire consent, loss to Follow up, or death.

In the event that the subject withdraws from the study every effort should be made to obtain full information on any on-going adverse events.

The reason for withdrawal must be recorded in the End of Study (EoS) CRF and in the patient file. All open adverse events should be closed or documented as ongoing. Data collected up to the point of subject withdrawal may be used, unless any local regulations prohibits the use of the data.

2.6. Study Procedures

2.6.1. Screening and Informed Consent

Patients who may be eligible for enrollment will go through the informed consent process. At the screening visit, subjects will be approached to obtain written informed consent prior to any study specific procedures being performed. The purpose of the study and the benefits and risks of the procedures will be explained to the subject and the consent process must be documented accordingly in the medical record. Subjects who agree to study participation must sign an approved ICF. Subjects will be informed that their participation in this study is voluntary and they may refuse to participate or discontinue from the study at any time. Subjects will be given the opportunity to ask questions so that

they are adequately informed about the research. A copy of the signed informed consent must be provided to the subject and the informed consent process will be documented in source documents. Subjects are considered enrolled once their informed consent has been correctly documented.

If new information becomes available that may affect a subject's decision to continue to take part in the study, this information will be discussed with the subject.

Subjects who are unable or unwilling to provide written informed consent should not be included in the investigation.

The following assessments/procedures will be performed during the screening, following the institutions' standard protocols:

- Demographics
- Medical history
- Physical examinations
- Concomitant medications
- Presence/history of atrial fibrillation
- Previous and current treatments of atrial fibrillation

2.6.2. Intervention

Patient management and treatment decisions are at the discretion of the care team per routine clinical practice. The KODEX-EPD system is an open-platform system however all catheters/leads used during the intervention need to be calibrated prior to the intervention.

2.6.2.1.Clinical Workflow

- 1) Advance the Achieve spiral mapping catheter (Achieve) to the Left Atrium (LA).
- 2) Image the LA with the Achieve by maneuvering the catheter around the LA under different angles.
- 3) Inflate the Cryoballoon (CB) and advance CB to occlude the ostium, make sure the location of the Achieve is maximal 15 mm distal to the CB. Hold this location for 5 seconds.
 - KODEX-EPD System will obtain a "shadow" of the Achieve at the current location this will take approximately 2 seconds.

Please note that there are 2 types of notifications on the KODEX-EPD system that can be shown when obtaining the 'shadow';

- **DTM; When the distance between the Achieve and the Mesh is > 10mm**
- **DTO; When the distance between the Achieve and the Ostium is > 35mm**

It is recommended to reposition the catheter and acquire a new shadow

- 4) Verify occlusion on fluoroscopy (in the blinded arm) or KODEX(in the KODEX guided arm) by selective contrast injection while simultaneously stepping on the KODEX-EPD System's foot pedal/or the injection button in the KODEX-EPD system is pressed to start the occlusion

assessment with the KODEX-EPD System. The occlusion assessment will take approximately 12 seconds. After which the physician should decide to;

- Proceed with CB ablation and move to next PV
- Reposition CB and repeat step 4.

Please note that for a successful occlusion assessment on the KODEX-EPD system it is important that;

- ***The there is no DTM, DTO or DTS (When the distance between the Achieve and the Shadow is > 10mm) notification on the KODEX-EPD system***
- ***The injection on the KODEX-EPD system is synced with the actual injection***
- ***The Injection is done with one shot.***

If occlusion is not indicated when assessing occlusion in the KODEX guided arm it is recommended to reposition the CB and re-assess the occlusion with KODEX. In total 3 consecutive attempts should be made to obtain occlusion on KODEX.

It is recommended to use an auto-injector where 6cc is injected at 2.5ml/sec and the dye/saline ratio is between 50/50 to 100/0.

If a manual syringe is used the injection should be swiftly and the dye/saline ratio needs to be between 70/30 to 100/0. The amount of injection is at the physician's discretion.

Considerations for the use of contrast in this workflow are the following;

- The contrast injection induces a significant local dielectric change and impacts some/all readings off the Achieve electrodes.
- The contrast needs to reach and embed the Achieve electrodes.
- Monitor no movement during injection.
- The Achieve's proximity to the CB will impact the results.

2.6.2.2.Data Collection

The following data will be collected during the intervention:

- KODEX-EPD data collection
- Fluoroscopy system data collection
- Fluoroscopy time
- Fluoroscopy dose
- Number of contrast dye injections
- Contrast dye volume
- Information on durability of the PV isolation.

- Time to isolation (TTI) – if possible
- Number of ablations per vein
- Procedure time (skin to skin)
- cineloops of procedural images
- Cryoconsole freeze data
- Safety Events

2.6.3. *Follow up*

This is an acute study and there is no follow-up foreseen.

2.6.4. *Discharge & End of Study*

The End of Study (EoS) is defined as after patient's discharge. The following data will be collected during the Discharge/EoS visit;

- Vital signs
- Concomitant medication
- Safety Events

2.6.5. *After End of Study*

After the study participation has ended the subjects will be followed up at the discretion of the investigator in accordance with the standard of care. No additional follow up is intended after Subjects' participation in the study has ended.

Subject data may be collected after the subjects' end of study. Following the FDA guidance; all AEs and non-study related SAEs should be followed up until they have resolved or stabilized or until 30 days after participants' EoS. All other SAEs should be followed until resolution or until the condition has stabilized with no further change expected.

Data collected for the purpose of this study may be used for future clinical research in the area of cardiac ablations.

2.6.6. *Schedule of Assessments*

Table 1; Schedule of Assessments

	Screening	Intervention	Discharge/EoS
Visit window	≤ - 1 month	-	-
Informed consent	X		
Medical History	X		
Physical Examinations	X		
Vital Signs	X	X	X
Demographics	X		
Incl./Excl. Criteria	X		

TEE	x ¹	x ²	
12-Lead ECG	x ¹	x ²	
Fluoroscopy time and dose		x ³	
Contrast dye # of injections and volume		x ³	
TTI		x	
# of Ablations per PV		x	
Procedure time		x	
cineloops of procedural images		x	
Cryoconsole freeze data		x	
Concomitant Medications	x	x	x
(S)AE reporting	x	x	x

¹ Only collect data when assessment is done per standard of care within 1 months of screening. Assessment doesn't require to be done for the purpose of the study.

² Only collect data when assessment is done per standard of care. Assessment doesn't require to be done for the purpose of the study.

³ Data from 2 intervals;

1. start of procedure – transseptal puncture
2. successful transseptal puncture – isolation

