2.2.2. Primary Endpoints

1. The accuracy, sensitivity, specificity and positive and negative predictive values of the KODEX-EPD PV occlusion feature as compared to conventional angiographic method of fluoroscopy with contrast dye that will be used to guide the procedure.
2. The success of the freeze when freeze is initiated based on the assessment of the KODEX-EPD PV occlusion feature as compared to the success of the freeze when freeze is initiated based on the assessment with fluoroscopy and contrast dye.

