5.2. Analysis Sets

The Primary Analysis Set (PAS) includes all successful occlusion tests. Successful is defined as a test for which;

- procedural data e.g.: KOPDEX-EPD system data, venograms, and notes are obtained.
- Presence of DTS, DTM or DTO notifications were documented before obtaining the shadow.

This analysis set will be used for the primary endpoint analysis.

The Secondary Analysis Set (SAS) includes all PVIs and ablations done. This analysis set will be used for the analysis of the secondary endpoints.

The ITT (intend to treat) PVs will be used as a secondary analysis of the secondary endpoints.

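### Primary endpoint 2 does not say how a guided-arm vein with three negative KODEX readings is counted; if such veins leave the KODEX side only and are harder to treat, the comparison would favour KODEX

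*Combined protocol and SAP*

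**What the plan says.** Step 4 of the workflow (section 2.6.2.1) gives both arms the same choice after an occlusion assessment: go ahead with the ablation, or "Reposition CB and repeat step 4". The guided arm has an added recommendation to move the balloon and check again on KODEX whenever the system does not show occlusion. The text then adds: "In total 3 consecutive attempts should be made to obtain occlusion on KODEX". No section says what happens after a third negative reading, and the blinded arm has no corresponding count. Section 2.6.2 also states: "Patient management and treatment decisions are at the discretion of the care team per routine clinical practice".

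Primary endpoint 2 (sections 2.2.2 and 5.1.1) is "The success of the freeze when freeze is initiated based on the assessment of the KODEX-EPD PV occlusion feature", compared with success when the freeze is "initiated based on the assessment with fluoroscopy and contrast dye".

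On who is analysed, section 5.2 says: "The Primary Analysis Set (PAS) includes all successful occlusion tests". A test is successful there if its data were obtained and its notifications documented, not if occlusion was shown. The same section adds: "The ITT (intend to treat) PVs will be used as a secondary analysis of the secondary endpoints". The exclusions from the primary analysis in section 2.2.1 do not mention veins that never show occlusion on KODEX. Section 5.4.2.1 says only that results are summarised by test, by vein and by patient. Section 5.5.1 rules out imputation.

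**The concern.** The denominator of endpoint 2 depends on something that happens after the vein has been assessed, namely which assessment led to the freeze. A vein that fails three KODEX attempts still belongs to a patient having an ablation, and the care team may freeze it on the venogram or on judgement. That freeze has no defined place on the KODEX side. One frozen on the venogram could even be made to fit the comparator wording.

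Such veins may be the ones that are hard to occlude. Leaving them out of one side only would raise the KODEX success rate through the choice of veins rather than through better guidance. Because the rule is not written down, the denominator of a primary endpoint could also be settled after the results are known. Section 1.3.3 gives this direct comparison as one of the reasons for the study.

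**Working it through.** **The plan's own figure.** Section 5.3 expects 80% success with a lower limit of about 70% and arrives at 87. The smallest n for which the exact (Clopper-Pearson) lower limit reaches 0.70 at an observed 0.80, with 2.5% in the lower tail, is 87 (limit 0.7005), so the figure reproduces. With 5% in the lower tail it would be 64, so the one-sided label does not match the number; that is a separate matter. About four veins per patient is inferred: 87/22 = 3.95 and 120/30 = 4.

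**Where a vein with three negative KODEX readings could go.**

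- Frozen anyway and counted in the guided arm: permitted by care-team discretion, and no selection arises.
- Frozen on the venogram: contrast is injected in the guided arm too (step 4), so this basis is available. Read literally, the freeze is then not KODEX-initiated.
- Frozen on judgement: it fits neither side of the endpoint.

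The plan does not choose among these. In the blinded arm the operator does not see the KODEX occlusion data (synopsis and section 2.1), so fluoroscopy is the only method of assessing occlusion that the protocol provides. Nearly every freeze there would be classed as fluoroscopy-initiated.

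**Illustrative size.** Assumptions, none of them from the documents except the 80%: true success over all veins is 80% in both arms; a share h of guided-arm veins is lost from the KODEX side only; success in those veins is s. The observed guided-arm success is then (0.80 − h·s)/(1 − h).

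| h | s = 20% | s = 40% | s = 60% | s = 80% |
|---|---|---|---|---|
| 5% | 0.79/0.95 = 83.2% (+3.2) | 0.78/0.95 = 82.1% (+2.1) | 0.77/0.95 = 81.1% (+1.1) | 80% (0) |
| 10% | 0.78/0.90 = 86.7% (+6.7) | 0.76/0.90 = 84.4% (+4.4) | 0.74/0.90 = 82.2% (+2.2) | 80% (0) |
| 20% | 0.76/0.80 = 95.0% (+15.0) | 0.72/0.80 = 90.0% (+10.0) | 0.68/0.80 = 85.0% (+5.0) | 80% (0) |

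The comparator stays at 80% throughout. If the veins are kept in the arm in which they were treated, the shift is zero for every h and s.

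**Effect on numbers.** 25 patients × 4 veins = 100 veins. Losing more than 13 of them leaves fewer than the planned 87.

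**Why failure scoring must apply to both arms.** If these veins were scored as failures in the guided arm only, its rate would be 0.80 − h·s. That is 79% for h = 5%, s = 20% (−1 point) and 68% for h = 20%, s = 60% (−12 points), a bias of similar size in the other direction.

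**The case against.** A reader might infer that the plan removes these veins from the KODEX side, keeps equally hard veins in the comparator, and so favours KODEX by design. The documents do not support that.

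- Nothing says the veins are dropped. Negative tests remain in the Primary Analysis Set, and section 2.2.1 does not exclude them. The text says three attempts should be made, not that KODEX assessment ends there.
- The comparator is conditional in the same way. A vein frozen without venographic occlusion has no defined handling either. What remains is a practical asymmetry: the guided arm has a second basis for freezing at hand, while the blinded arm in effect does not.
- Veins on which KODEX is falsely negative are in fact occluded and need not do worse. Losing those would not raise the KODEX rate.
- The data are not absent. KODEX files, fluoroscopy data, cineloops, cryoconsole data (section 2.6.2.2) and the physician's visual assessment in the procedural notes (section 2.6.7.3) allow partial reconstruction. However, no listed item records the basis of a freeze or the attempts per vein, and Table 1 collects contrast injections by procedure interval rather than by vein.
- The comparison is non-randomised and descriptive (section 5.4.1), and the sample size concerns a single proportion. No test or decision rule is affected. This limits the consequence but does not remove bias from the estimate.

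The two arms' instructions are not contradictory as they stand; the guided arm has an extra recommendation. The gap is that its end point is unstated and the difference between the arms is not explained.

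**Conclusion.** The concern holds as a conditional one. The plan leaves undefined how a vein with three negative KODEX readings, or its fluoroscopy counterpart, enters primary endpoint 2, and neither analysis set in section 5.2 closes the gap. A bias towards KODEX needs two things: such veins are lost from the KODEX side only, and they succeed less often than the rest. Under the assumed ranges it would be about +1 to +15 points. The documents supply neither the share of veins nor their success rate, so this is an illustration and not an estimate, and zero is possible. For scale, section 5.3 plans for only 10 points between the expected 80% and its lower limit of about 70%, so a shift of several points would matter to the reading of the result.

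**What to change.** 1. Add two fields per freeze, in both arms: the number of occlusion attempts before it, and its basis (KODEX occluded / venogram occluded / neither).
2. In section 5.4.2.1, analyse endpoint 2 by treated arm, with every attempted, otherwise evaluable vein in the denominator and its actual freeze outcome. Report veins frozen without occlusion shown by the arm's own method on a separate line in both arms. Add a sensitivity analysis that counts them as failures in both arms alike. Keep the comparison by basis of the freeze as a supporting analysis.
3. The sponsor and investigators should state in section 2.6.2.1 what follows the third attempt, and reconcile or justify the difference between the arms. No clinical rule is proposed here.

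The cost is two CRF fields and a few sentences in section 5.4.2.1. The guided-arm rate may come out slightly less favourable.

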2.6.7. Standardization of Study Procedures

2.6.7.1. Measurements of Vital Signs

Blood Pressure (BP) and Heart Rate (HR) measurements should be determined after the subject has been seated for at least 5 minutes. BP should be measured on both arms and the arm with the highest systolic reading at screening should be used for BP determination throughout the study. The subject's pulse should be measured for 30 seconds and the number should be multiplied by 2 to obtain HR.

2.6.7.2. Concomitant Medication

Targeted concomitant therapy and medications will be recorded on the CRF. The following groups of concomitant medications will be recorded;

- Anticoagulants
- Cardiovascular medications
- Antiarrhythmic medications/substances

2.6.7.3. Procedural Images

Cineloops of procedural images are to be created starting just prior to contrast injection for fluoroscopic verification of occlusion for a duration of 5 seconds and should include one respiratory cycle. A visual assessment of the occlusion should be made by the physician at that time and documented in the procedural notes. The images will be collected and reviewed for an independent assessment.

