2. EXPERIMENTAL PLAN

2.1. Study Objectives

The study objective is to evaluate the performance of the KODEX-EPD PV occlusion feature as compared to conventional venographic method of fluoroscopy with contrast dye in cryoballoon procedures that is used to guide the procedure. Performance will be calculated in terms of accuracy, sensitivity, specificity and positive and negative predictive values. In the blinded arm of this 2-armed study, the operator will be blinded for the PV occlusion data on the KODEX-EPD system, and this data will not be used for clinical guidance. In the KODEX guided arm the operator will use the KODEX-EPD system occlusion data to guide the procedure.

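### The guided-arm operator may also read the venogram, and the basis of each freeze is not among the listed data, so primary endpoint 2 may not isolate KODEX-initiated freezes

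*Combined protocol and SAP*

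**What the plan says.** Sections 2.2.2 and 5.1.1 define endpoint 2 as freeze success when the freeze is started on the KODEX assessment, compared with freeze success when it is started on fluoroscopy and contrast dye. Section 1.3.3 gives the lack of such a direct comparison as a reason for the study.

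On the guided arm, Section 2.1 states: "In the KODEX guided arm the operator will use the KODEX-EPD system occlusion data to guide the procedure". Step 4 of the workflow in Section 2.6.2.1 reads "Verify occlusion on fluoroscopy (in the blinded arm) or KODEX(in the KODEX guided arm) by selective contrast injection", so contrast is given in both arms and only the method of verification differs. Of the KODEX run, the same step says "The occlusion assessment will take approximately 12 seconds"; the choice between freezing and repositioning is placed afterwards. Section 2.6.2 opens with "Patient management and treatment decisions are at the discretion of the care team per routine clinical practice".

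On the venogram, Section 2.6.7.3 asks for a cineloop and adds: "A visual assessment of the occlusion should be made by the physician at that time and documented in the procedural notes". Table 1 in Section 2.6.6 schedules cineloops with no arm restriction. Section 5.2 admits a test to the Primary Analysis Set when "procedural data e.g.: KOPDEX-EPD system data, venograms, and notes are obtained", and uses that set for the primary endpoint analysis without separating the two endpoints or the two arms.

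**The concern.** Masking runs one way. The blinded-arm operator is kept from the KODEX result, but no section keeps the guided-arm operator from the venogram. Where the two methods agree, this does not matter. Where they disagree, the operator may hold back a freeze that KODEX supports, or start one that KODEX does not support. The plan does not say how such a freeze is classified. Nor does it say on what basis a freeze begins if the three recommended KODEX attempts do not show occlusion.

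The items listed in Section 2.6.2.2 include KODEX data, cineloops and cryoconsole freeze data, but not the reason for starting a freeze. A freeze prompted or filtered by the venogram could therefore be reported as KODEX-initiated. Filtering would tend to pull guided-arm success towards that of the fluoroscopy arm. The trial could then report a guided-arm success rate that does not describe KODEX used alone, with no way for a reader to tell.

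**Working it through.** **1. The plan's own figure.** Section 5.3 gives 87 for endpoint 2, from an expected 80% and a lower bound of about 70%. The smallest n whose exact (Clopper-Pearson) lower limit of a two-sided 95% interval reaches 0.70 at an observed 0.80 is 87 (lower limit 0.7005), so the figure reproduces. 87 / 4 = 21.75, about 22 subjects, which implies four observations per subject, or about one per vein. Section 5.3 calls the method one-sided, and a one-sided 95% exact limit would give 64. That is a separate matter and does not affect this point.

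**2. The passages side by side.**

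- *If Section 2.6.7.3 covers both arms:* the guided-arm operator reads and documents the venogram for the same injection that KODEX is assessing, and can have both results when deciding.
- *If it covers only the blinded arm:* nothing in the workflow text secures a guided-arm venogram, although Table 1 schedules cineloops for all. Section 5.2 lists venograms as qualifying data with no arm exemption, so guided-arm tests without one may be left out of the set that serves endpoint 2.

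Each reading leaves a gap, and the text does not choose between them.

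**3. Timing.** The cineloop lasts 5 seconds and the KODEX assessment about 12. A reading made during the loop would come roughly 12 − 5 = 7 seconds before the KODEX result. This order is inferred from two durations. The point does not need it, because the decision follows the KODEX assessment and both results can be in hand by then.

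**4. How many tests could be affected.** Section 1.3.1.1 reports agreement with venography of 92.1% (baseline workflow) and 90.4% (injection workflow), from a retrospective database and per occlusion event. Assume that this carries over, with one test per vein:

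- 87 × (1 − 0.921) = 6.9
- 87 × (1 − 0.904) = 8.4

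So about 7 to 8 of 87 tests would be discordant.

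**5. How many could be vetoed.** A veto acts only on tests that are KODEX-positive and venogram-negative. For illustration, assume sensitivity = specificity = 0.904 and venographic occlusion in 50% to 70% of tests; neither assumption is in the documents.

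- At 50%: 0.50 × 0.096 = 4.8% of tests, or 87 × 0.048 = 4.2
- At 70%: 0.30 × 0.096 = 2.9% of tests, or 87 × 0.0288 = 2.5

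The remaining discordant tests are KODEX-negative and venogram-positive. They matter only if the operator freezes despite the KODEX result.

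**The case against.** A reader might infer that the guided-arm operator must read the venogram before KODEX answers, so that endpoint 2 by design compares venography plus KODEX with venography. The documents do not say this. Section 2.6.7.3 says should, not must, and its first sentence ties the loop to fluoroscopic verification: "Cineloops of procedural images are to be created starting just prior to contrast injection for fluoroscopic verification of occlusion for a duration of 5 seconds". Step 4 of Section 2.6.2.1 gives that verification to the blinded arm. Collecting a loop does not oblige the operator to read it live, and no order of reading is stated. The study schematic is not available and might separate the workflows. What remains is an unresolved scope and the absence of any masking to the venogram.

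A reader might also infer that Section 5.2 strictly excludes every test without a venogram and could empty the guided arm. Its list is introduced as examples, so exclusion is a risk and not a stated rule.

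A third temptation is to put a size on the bias. Take the assumptions of step 5, with freeze success of 85% in occluded veins and 30% to 50% otherwise. Freezing on KODEX alone then gives 0.904 × 0.85 + 0.096 × 0.30 = 79.7% at the low end and 0.9565 × 0.85 + 0.0435 × 0.50 = 83.5% at the high end. A complete veto gives 85%, a shift of 1.5 to 5.3 points. Only the 90.4% is documented. The rest, including a 100% veto and error-free venography, is supplied. Nor should the shift be set against the 80% to 70% gap, which is a one-arm precision target.

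Disagreement between the methods is also not the only source of arm differences. The study is non-randomized, with the blinded arm at two centers and the guided arm at one, so center, operator and case mix can differ. With 87 and 120 observations at 80%, the 95% half-width for a difference is 1.96 × √(0.16/87 + 0.16/120) = 11 points even before clustering, and Section 5.4.1 plans no inference.

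Finally, KODEX data, loops and freeze data are collected and the images are independently reviewed, so discordance could be tabulated afterwards. That is true, but such a table would not show why a freeze was started or withheld. The case report form pages are not in the documents, so a suitable field may exist; the listed data items do not include one.

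**Conclusion.** The point holds as a possible contamination that the plan neither prevents nor records. Endpoint 2 may count as KODEX-initiated some freezes that were influenced by venography or started after KODEX did not indicate occlusion. On the narrower reading of Section 2.6.7.3, it may instead lose guided-arm tests that lack a venogram.

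The documents do not give the size of the effect. The only figure anchored in them is about 7 to 8 discordant tests in 87. It rests on the retrospective agreement carrying over and on one test per vein, and only some of those tests could be vetoed. The finding concerns what endpoint 2 can be said to measure; it does not show that the result will be wrong. It is a cheap improvement.

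**What to change.** - Reconcile Sections 2.6.2.1, 2.6.7.3 and 5.2. State whether the visual reading and the venogram condition apply in the guided arm, and define the primary set for endpoint 2 separately by arm.
- For each guided-arm freeze, record on the case report form, at the time of the procedure, the KODEX result, the basis of the decision and whether KODEX was overridden.
- Report endpoint 2 for all guided-arm freezes together with the override count, and separately for freezes started on a KODEX occluded result without override.
- If the venogram stays available to the operator, describe endpoint 2 as KODEX guidance with venography available versus venography alone.

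Whether the operator may view the venogram is a clinical matter for the sponsor and investigators, and nothing here prescribes it. The cost is some protocol wording and a few form fields, with no added procedure. The downside is that the guided-arm claim may be narrower. The basis of a freeze should be captured during the procedure, since it may not be recoverable later.
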